## 1. Introduction

Indicators show that infections caused by antimicrobial resistant organisms continue to increase in Canada,i and despite decades of antimicrobial stewardship programs the quality of antibiotic prescribing remains suboptimal.ii-iv Continued efforts to preserve the effectiveness of antimicrobials to treat infectious diseases are essential, since misuse of antimicrobials is the primary mechanism driving resistance.v-viii The treatment of cystitis is one indication where a change in antibiotic use was necessary. Uncomplicated acute cystitis (UAC) is the most prevalent form of urinary tract infection in women, and is most commonly caused by *escherichia coli* (E. coli).ix,x UAC is a common indication for antimicrobial treatment in healthy, non-pregnant women.xi,xii E. coli resistance to TMP-SMX and fluoroquinolones, historically the antibiotics most often used for UAC, has exceeded 20% in all areas of British Columbia, thus limiting the empirical effectiveness of these treatments. Due to increased resistance, Nitrofurantoin is now the best evidence supported treatment of infections caused by E. Coli or Staphylococcus Saprophyticus.xiii

## 2. Purpose

### Study Purpose

To conduct a randomized trial testing the effectiveness of personalized prescribing portraits and therapeutic letters on appropriate treatment for uncomplicated acute cystitis.

### Research Question(s) / Hypothesis

Research Question: Determine the change in nitrofurantoin prescribing associated with the personal prescribing portrait and the therapeutics letter for UAC.

Hypothesis: The personal prescribing feedback portrait and the letter will each be associated with an increase in nitrofurantoin prescribing.

### 3. Objectives

To conduct a randomized trial testing the effectiveness of personalized prescribing portraits and therapeutic letters on appropriate treatment for uncomplicated acute cystitis.

### 4. Methods

We conducted a randomized trial to analyze the effectiveness of a personalized prescribing portrait in the primary care setting in the province of British Columbia between September 2021 and March 2022.

Physicians are randomized to three groups:

	Arm A ~33%	Arm B ~33%	Arm C ~33%
Initial mailing Sept 23, 2021	Early Portrait + Letter	Nothing	Early Letter Only
Delayed mailing Mar 28, 2022		Delayed Portrait + Letter	Delayed Portrait + Letter

\*Approximately 1,691 physicians were randomized to each group. However, not all will receive materials due to opt-outs and incorrect addresses.

#### Study Dates:

- Early mailing (groups A and C): 23-Sept-2021
- Delayed mailing (groups B and C): 28-Mar-2022
- Letter & Portrait topic released publicly on website: 28-Mar-2022

**Study Period:** September 24th, 2021 to March 28, 2022.

**Delay Period:** March 29, 2022 to Sept 28, 2022

#### Study Comparisons:

[figure not shown]
There will be four comparisons:

During the study period (Sept 23, 2021 to Mar 28, 2022):

- Arm A vs Arm B (impact of L+P combined)
- Arm A vs Arm C (The added impact of P in physicians who received L)
- Arm C vs Arm B (Impact of L)

During the study period (Sept 23, 2021 to Sept 28, 2022):

- Arm B vs Arm C (repeated messaging)

## Data sources

B.C. Ministry of Health *Healthideas* data warehouse, including: ClaimsHist, MSP fee-for-service, hospital discharge abstracts, client roster, physician roster.

Estimated number of records/charts to be examined: 1691 physicians randomized to each group = 5,073. Estimate 6 UTI treated visits per physician = **30,438 patient records** to be included in the analysis.

## Population (cohorts)

### Physicians:

Physician eligibility criteria for randomization:

- i. Registered with the College of Physicians and Surgeons of B.C. (CPSBC)
- ii. Defined as a *General Practitioner* or *FP – Emergency Medicine* according to the B.C. Ministry of Health’s Medical Services Plan (MSP) with a license status of *private practice, temporary license, salaried, or post graduate*.
- iii. Valid mailing address in B.C according to the College of Physicians and Surgeons of British Columbia’s public physician information.
- iv. Had  $\geq 100$  prescriptions filled at a community pharmacy in 2020 according to PharmaNet claims.

\*Approximately 1,691 physicians were randomized to each of the 3 study groups.

Physician eligibility criteria to receive a prescribing portrait:

- i. Met the criteria for randomization above
- ii. Diagnosed  $\geq 1$  eligible patient with UAC in 2019 or 2020 (for delay group: 2020 to 2021)

**Patients:**

Patient visits for UAC were identified from MSP billing records in which the first 3 digits of the ICD-9 diagnosis code in the record indicated 595 - Cystitis.

Include UTI codes:

1. 595, 595.0, 595.3-595.9 (cystitis) (but do not include 595.1, 595.2 chronic cystitis)
2. 599 or 599.0, 599.8, 599.9 UTI, site not specified (do not include if 599.1-599.7)
3. 788 or 788.9 or 788.1 symptoms involving urinary system or dysuria (do not include if 788.0, 788.2-788.8)
4. 596, 599.7, or 791

These UAC patients were then categorized according to whether they received antibiotic treatment on or within 5 days of the physician office visit recorded in the MSP billing record. Only count events where the diagnosing and prescribing physician are the same.

**Patient exclusions:**

- less than 77 days (2.5 months) MSP enrolment in the 91 days prior to visit
- Age <15 at time of UTI diagnosis
- Male or missing sex
- Recurrent UTI:
  - A visit with a diagnosis of UTI in the prior 90 days, and/or
  - More than 4 visits in the 1095 days (3 years) before visit with a diagnosis of UTI
- Complicating factors:
  - Discharge from hospital in prior 30 days
  - Severe disease/infection of the kidney (pyelonephritis), ICD9: 590, 590.1, 590.2, 590.8, 590.9; ICD10: N10, N12, N15.1, N16 (within previous or following 10 days). Hospital admission or ED.
  - Indwelling catheter, based on ICD-9: V53.6, 996.64, 996.76, 996.31. ICD10: T83.0x, Z46.6, Z96.0, in 91 days prior to UTI diagnosis
  - Impaired renal function, fee item: 33758, 33723, 33759, 33761 or if they have a visit with a nephrologist (prior 365 days)
  - Structural and functional abnormality of urinary tract (prior 365 days) [ICD9: 16.9, 137.2, 997.5, 939.3, 939.9, 947.4, V130 ICD10: A181, B901, N998, N999, T198, T199, T283, T288, Z874.]
  - Pregnant women, fee item: 14090, 14091, 36360, 36361, 04717 codes or ICD 646.6, V22.x, V23.x in the 270 days before the UTI visits + no record of pregnancy outcome after pregnancy code and before UTI event (ICD9 630.x, 631.x, 632.x, 633.x, 634.x, 635.x, 636.x, 637.x, V24.x, V27.x, 656.4 or ICD10 O00.x, O01.x, O02.x, O03.x, O04.x, O05.x, Z37.x, O36.4x)

- Diagnosis of STI within 14 days before or after UTI visit (ICD9: 090-099, ICD10: A50-A64)
- Chronic Kidney Disease (ICD9: 585.x, ICD10: N18) MSP complex care code: N585, R585, I585, H585, D585, C585, K573) in previous 365 days
- Physician visit where patient had any oral, intravenous, or injection antibiotics (ATC: J01) in previous 91 days dispensed by any physician
- Patients with a dispensation under Plan P or B (on abx fill date or within 3 months after)

### Exposures

Female patient visits for UAC identified from physician MSP billing records in which the first 3 digits of the ICD-9 diagnosis code in the record indicated 595 – *Cystitis*.

### Medications

All oral formulation prescription antibiotics available in BC were included in the portrait.

Nitrofurantoin identified using ATC: J01XE01

### Outcomes

The primary outcome is the incidence of women treated with nitrofurantoin in the 5-day period following a diagnosis of Uncomplicated Acute Cystitis, including the day of diagnosis.

## 5. Statistical Analysis Plan

1. **Baseline Characteristics:** Physicians and Patients by Study Group. Age (mean, sd), age groups, sex, urban vs rural.
2. **Trends:** Weekly prescribing line chart by randomized physician group of Nitrofurantoin, Ciprofloxacin, and TMP-SMX, from 6 months prior to first mailing to the end of the delay period - 6 months after the delayed mailing (September 2022). This will illustrate background trends in prescribing patterns.
3. **Relative Risk:** Prescribing in the early and delayed intervention groups will be compared 6 months pre/post intervention. A 4-way comparison of numerators during the pre/post periods between the early and delay groups will provide an odds ratio that approximates the relative risk.xiv,xv Do this for each of the four study comparisons listed in Section 4.

Acute cystitis episodes = n

Outcome Measures	Expected Change	Intervention Physicians				Delayed Control Physicians				Crude OR	Adjusted OR	95% CL
		Time Period		Time Period		Time Period		Time Period				
		Pre		Post		Pre		Post				
		YES	NO	YES	NO	YES	NO	YES	NO			
Nitrofurantoin	+	a	b	c	d	e	f	g	h			
Ciprofloxacin	-											
TMP_SMX	-											
Other	-											
No Treatment	n/c											

$$\text{Crude OR} = \frac{(c * h)}{(g * d)}$$

Evaluation is a 4-way comparison: the ratio of change in the early group between pre and post intervention is compared to the same ratio of change in the delayed group.

$$\text{Adjusted OR} = \frac{\text{Crude OR}}{\frac{(a * f)}{(e * b)}}$$

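### Section 5, item 3 uses pre-period prescribing only by dividing one odds ratio by another; entering it as a physician-level covariate would give a more precise estimate

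*Combined protocol and SAP*

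**What the plan says.** Section 4 makes the physician the unit of allocation: "Physicians are randomized to three groups". Section 5, item 1 names the characteristics to be described for physicians and patients by study group: "Age (mean, sd), age groups, sex, urban vs rural". They appear nowhere else in the analysis.

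Item 3 sets out the effect estimate: "Prescribing in the early and delayed intervention groups will be compared 6 months pre/post intervention". The Crude OR is the post-period odds ratio, (c × h)/(g × d). The Adjusted OR is that figure divided by the pre-period odds ratio, (a × f)/(e × b). The accompanying text confirms the intent: "the ratio of change in the early group between pre and post intervention is compared to the same ratio of change" in the delayed group. The cells are counts of cystitis episodes pooled over all physicians in an arm. The instruction covers every contrast: "Do this for each of the four study comparisons listed in Section 4".

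No regression model or covariate is named. The results table has a column for 95% confidence limits, but no variance method is given for it. The only size information is under Data sources in Section 4 ("Estimate 6 UTI treated visits per physician"), which does not say whether the 6 visits are per period or in total.

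**The concern.** A reader who meets a column headed Adjusted OR would expect adjustment for baseline differences. What the plan provides is the removal of the pre-period odds ratio at full weight. In a randomised comparison the pre-period odds ratio has expectation near 1, so dividing by it is not needed for validity. Its purpose is precision, and it serves that purpose only if a physician's prescribing before the mailing predicts prescribing afterwards well enough to pay for the added noise. With few visits per physician, that is doubtful.

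The stake is the width of the interval in all four comparisons, including A versus C and C versus B, which separate the portrait from the letter. Because physicians were randomised and episodes are counted, an interval computed from pooled counts as if visits were independent would also fail to reflect the clustering.

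**Working it through.** **Inputs from the documents.** 1,691 physicians per arm and 6 visits per physician (Section 4, Data sources); the Crude and Adjusted OR formulas (Section 5, item 3).

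**Not in the documents, so assumed.** Visits per period (6, with 3 as a check), ICC (0.05, 0.10, 0.20) and the baseline nitrofurantoin rate.

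**1. The plan's own figures.** 3 × 1,691 = 5,073 physicians, and 5,073 × 6 = 30,438 records. Both match. There is no power calculation to reproduce.

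**2. What the Adjusted OR is.** log(Adjusted OR) = log[(c × h)/(g × d)] − log[(a × f)/(e × b)]. It is a difference in differences on the log-odds scale, with the coefficient of the pre-period fixed at 1.

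**3. Benchmark with independent visits.** Take an assumed 50% rate and 1,691 × 6 = 10,146 visits per arm and period. The standard error (SE) of the log Crude OR is √[2/(10,146 × 0.25)] = 0.0281. For the log Adjusted OR it is √[4/(10,146 × 0.25)] = 0.0397. The division doubles the variance if physicians' habits do not persist.

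**4. With a stable physician effect.** Let m be visits per period. In units of the variance of a single visit's outcome, on a linear scale with equal visit counts:
- Variance of a physician's post-period share: T = ICC + (1 − ICC)/m
- Pre/post correlation of shares (also the reliability of the pre-period share): r = ICC/T
- No adjustment: T
- Change-type contrast: 2(1 − ICC)/m = 2T(1 − r)
- Regression on the pre-period share: T − ICC²/T = T(1 − r²)

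For m = 6:

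| ICC | r | No adjustment | Change-type (plan) | Regression | Plan ÷ regression |
|---|---|---|---|---|---|
| 0.05 | 0.24 | 0.208 | 0.317 | 0.196 | 1.61 |
| 0.10 | 0.40 | 0.250 | 0.300 | 0.210 | 1.43 |
| 0.20 | 0.60 | 0.333 | 0.267 | 0.213 | 1.25 |

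The last column equals 2/(1 + r). The change-type contrast beats no adjustment only when 2(1 − r) < 1, that is, when r > 0.5. Regression is never worse than either. At ICC 0.10, 5,073 physicians analysed by regression match about 5,073 × 0.300/0.210 ≈ 7,250 analysed by the planned ratio.

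**5. Fewer visits.** If the 6 visits are the total over both periods (m = 3), r is 0.14, 0.25 and 0.43. The planned contrast then has 76%, 60% and 40% more variance than regression, and is worse than no adjustment at all three ICCs.

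**6. Simulation on the odds-ratio scale.** There were 1,691 physicians per arm, 12 scenarios and 150 replicates each. The settings were 3 or 6 visits per period, physician random-effect SD 0.5 or 1.0, covariate log-odds coefficient 0, 0.1 or 0.3, and conditional log OR 0.2. Entering the physician's pre-period rate as a covariate raised estimate/SE by 7% to 40% over the planned ratio. Adding age, physician sex and rurality to the pre/post model changed estimate/SE by −1% to +2% and multiplied the SE by 0.99 to 1.05. With 150 replicates, small differences are not resolved.

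**7. Demographics on top of baseline share.** Repeat step 4 with the between-physician variance reduced by the fraction the covariates are assumed to explain. At 10% to 30%, residual variance falls by 1.5% to 5.8%, or about 0.8% to 3% of the SE. At 1% to 5%, it falls by 0.15% to 0.87%.

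**The case against.** The planned ratio is a recognisable pragmatic-trial measure, and randomisation keeps it valid. The complaint is about efficiency only. If physicians' habits are persistent enough, the ratio does help: at ICC 0.20 with 6 visits its variance is 0.267, against 0.333 unadjusted. All the sizes above depend on assumed values. These points stand, and for that reason the conclusion is a range. They do not rescue the division, because regression has the smaller variance at every value tried.

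Regression on a physician's own share is also not costless. Under Population in Section 4, an eligible cystitis patient was a condition for receiving a portrait but not for being randomised. Some randomised physicians may therefore have no pre-period visit and an undefined share, whereas pooled counts keep their post-period visits. This stands and must be met by a stated rule.

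A reader might go further and infer that adjusting for the tabulated characteristics is a free gain in precision. The documents do not support that:
- They give no figure for how well these variables predict nitrofurantoin choice.
- Patient sex cannot vary, since the exclusions remove "Male or missing sex"; only physician sex can.
- Stable physician traits such as sex and rurality appear in both periods, so their imbalance largely cancels in the planned ratio.
- Covariates in a logistic model generally do not shrink the SE of a log odds ratio. They change the estimand from marginal to conditional.

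Nor do the documents support the inference that A versus C and C versus B lose most. The arms are of about equal size, so the proportional loss is the same in each contrast, and no expected effects are stated.

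**Conclusion.** The point holds as one about how pre-period prescribing enters the estimate. Under 6 visits per physician per period and an ICC of 0.05 to 0.20, the planned ratio has 25% to 61% more variance than regression on the physician's pre-period share, or an SE about 12% to 27% larger (√1.25 to √1.61). At ICC 0.05 and 0.10 it is also noisier than no adjustment, by 52% and 20% in variance; at 0.20 it is 20% better. These figures use a linear scale and equal visit counts. The documents supply neither an ICC, a baseline rate nor visits per period, so no single figure can be attached to this trial.

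The planned estimate is not biased by this choice. The tabulated demographics are a secondary matter: any extra gain from them is probably small and cannot be quantified from the documents.

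**What to change.** In Section 5, item 3, make the main estimate for each comparison a prespecified regression of the post-period nitrofurantoin outcome on arm and the physician's pre-period nitrofurantoin share. Measure the share before the first mailing, so that no arm's baseline can be affected by the materials. Cluster standard errors by physician, and state this as the method for the 95% limits. Report a standardised risk difference and risk ratio, and say that these are marginal effects.

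State a rule that keeps physicians with no pre-period visit, such as a missing-baseline indicator with a constant fill for the share. Keep the crude and ratio-of-odds-ratios table as descriptive. Patient age group, physician age, physician sex and urban/rural may be listed as secondary covariates, with coding and missing-data handling fixed in advance.

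The cost is a few more lines of plan and code, the missing-baseline rule, and a change in the headline effect measure from an odds ratio. The pre-period counts are already required for the planned table, so no new data source is needed.

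### SAP item 3 presents an odds ratio and a ratio of odds ratios as approximating a relative risk, but the plan does not show that this holds for nitrofurantoin

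*Combined protocol and SAP*

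**What the plan says.** Section 5, item 3 carries the title *Relative Risk*. It says that the pre/post comparison of early and delayed groups "will provide an odds ratio that approximates the relative risk", and cites two references for that claim. It describes the calculation as "A 4-way comparison of numerators during the pre/post periods", and further down explains that "the ratio of change in the early group between pre and post intervention is compared to the same ratio of change in the delayed group".

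The table shell holds eight counts of cystitis episodes with and without each outcome: a/b (pre) and c/d (post) for intervention physicians, e/f (pre) and g/h (post) for delayed controls. The result columns are labelled Crude OR, Adjusted OR and 95% limits. The printed formulas are:

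- Crude OR = (c × h)/(g × d)
- Adjusted OR = Crude OR ÷ [(a × f)/(e × b)]

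Item 3 is to be repeated for each of the four comparisons in Section 4. The Outcomes paragraph of Section 4 reads: "The primary outcome is the incidence of women treated with nitrofurantoin in the 5-day period following a diagnosis". Nowhere do the documents give an expected nitrofurantoin share, a condition for the approximation, or a formula for a risk ratio or risk difference.

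**The concern.** The title and the approximation clause tell the reader to treat the result as a relative risk. The formulas use all four NO counts and yield an odds ratio and a ratio of odds ratios. These come close to a relative risk when few episodes have the outcome or when the effect is very small. The plan asserts the approximation without showing that either condition applies. The Introduction presents nitrofurantoin as the treatment with the best supporting evidence, so a low share cannot be presumed.

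The research question is how much nitrofurantoin prescribing changes, and the primary outcome is an incidence. If the item 3 result is read as a ratio of incidences, the change will look larger than it is by an amount that the plan gives no means of judging in advance.

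**Working it through.** **Inputs.** The cells a to h and both formulas come from Section 5, item 3. The plan states no effect estimate, target effect or nitrofurantoin share, so it has no figure of its own to reproduce here. Every share below is an assumption.

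**Step 1: what the formulas are.** Crude OR = (c × h)/(g × d) = (c/d)/(g/h), the ordinary post-period odds ratio. Dividing by (a × f)/(e × b) = (a/b)/(e/f) gives

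Adjusted OR = [(c/d)/(a/b)] / [(g/h)/(e/f)],

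which is a ratio of odds ratios.

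**Step 2: distance from the risk ratio.** Let p = g/(g+h) and q = c/(c+d), and take equal pre-period shares, so that Crude OR = Adjusted OR. Then

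- RR − 1 = (q − p)/p
- OR − 1 = (q − p)/[p(1 − q)]
- (OR − 1)/(RR − 1) = 1/(1 − q)
- OR/RR = (1 − p)/(1 − q)

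**Step 3: numbers for an assumed 5-point gain.**

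| Control p → intervention q | RR | OR | OR/RR | (OR−1)/(RR−1) |
|---|---|---|---|---|
| 10% → 15% | 1.50 | 1.59 | 1.06 | 1.18 |
| 20% → 25% | 1.25 | 1.33 | 1.07 | 1.33 |
| 30% → 35% | 1.17 | 1.26 | 1.08 | 1.54 |
| 50% → 55% | 1.10 | 1.22 | 1.11 | 2.22 |
| 70% → 75% | 1.07 | 1.29 | 1.20 | 4.00 |

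For example, at 50→55%: RR = 0.55/0.50 = 1.10 and OR = (0.55/0.45)/(0.50/0.50) = 1.22.

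**Step 4: near the null.** With RR = 1.02, the OR is 1.022 at a control share of 10% (q = 10.2%) and 1.041 at 50% (q = 51%). The absolute gap is small in both cases.

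**Step 5: unequal pre-period shares.** If the intervention arm goes 40→44% and the control arm 50→55%, both rise by a factor of 1.10 and the ratio of risk ratios is 1.00. The Adjusted OR is [(0.44/0.56)/(0.55/0.45)] / [(0.40/0.60)/(0.50/0.50)] = 0.643/0.667 = 0.964. With a smaller imbalance, 49→53.9% against 50→55%, it is 0.996. So under imbalance the two measures need not share a null, but randomization makes a large imbalance unlikely.

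**The case against.** The best defence is that an analyst would know exactly what to compute. The formulas are explicit, the columns are labelled OR, and all eight counts are shown, so any reader of the completed table can derive a risk ratio. The plan says the odds ratio approximates the relative risk, not that it equals it, and cites two references that may state the conditions. All of this stands, and it makes the point one of scale and interpretation. The cited papers cannot be consulted here, so nothing is claimed about what they show. The plan's own text still states a property that its formula does not have in general.

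A reader might also infer that the wording sets up a second, competing measure built from the YES counts alone, (c/a)/(g/e). The documents do not support that. The sentence about the ratio of change does not say whether counts, risks or odds change; read as odds, it is identical to the printed Adjusted OR (Step 1). The reference to numerators is one loose word beside explicit formulas. It needs correcting, but it is not evidence of a different planned analysis.

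Finally, the ratio of excesses in the last column of the table is the more striking scale. On the OR/RR scale, the same 5-point examples differ by only 6% to 11% for control shares of 10% to 50%.

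**Conclusion.** The point holds as a mismatch between the measure named and the measure calculated. Item 3 claims closeness to a relative risk, and its formulas have that property only under conditions that the plan does not establish for nitrofurantoin. With balanced pre-period shares, the result lies further from 1 than the risk ratio by the factor 1/(1−q): about 1.2 if 15% of intervention-arm episodes are treated with nitrofurantoin, and about 2.2 if 55% are. Which of these is nearer the truth is unknown, because the documents give no share.

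Two stronger readings should be avoided. One is that the analysis is invalid: the odds ratio and ratio of odds ratios are algebraically sound and, with balanced pre-period shares, OR = 1 exactly when RR = 1, so the null and the direction of effect are unaffected. The other is that the nitrofurantoin effect will be overstated by some given multiple: every multiple above rests on assumed shares, and the gap is small if the share is low or the effect slight. The labelling point is certain, but its numerical consequence for the primary outcome is not.

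**What to change.** **Wording.** Label item 3 and its results as an odds ratio and a ratio of odds ratios. Delete the clause about approximating the relative risk. Replace the reference to numerators with wording that matches the YES/NO formulas.

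**Added measures, for the primary outcome (nitrofurantoin) only:**

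- Risk ratio: [c/(c+d)] / [g/(g+h)]
- Adjusted risk ratio: the risk ratio ÷ {[a/(a+b)] / [e/(e+f)]}
- Risk difference: c/(c+d) − g/(g+h)
- Adjusted risk difference: the risk difference − [a/(a+b) − e/(e+f)]

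State which measure is primary.

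**Confidence limits.** Physicians are the randomized units, and the Data sources section expects about 6 treated visits from each. The limits should therefore account for clustering by physician, for example by resampling physicians with both of their periods together. Limits from the eight pooled counts alone would ignore that clustering.

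**Cost.** The point estimates come from counts already in the table shell. The clustered limits need the episode data kept by physician, which the plan already requires because it links each episode to a single diagnosing and prescribing physician. No new data collection is needed. The downside is a little more analysis and a headline ratio that will generally be closer to 1.

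### Physicians are randomised, but item 3 of the analysis plan works from pooled episode counts and names no method for its 95% limits, so clustering by physician and pre/post pairing are left unaddressed

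*Combined protocol and SAP*

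**What the plan says.** - **Unit of randomisation.** Section 4 (Methods): "Physicians are randomized to three groups". Under Physicians: "Approximately 1,691 physicians were randomized to each of the 3 study groups".
- **Nesting.** Under Patients: "Only count events where the diagnosing and prescribing physician are the same". Each counted event therefore belongs to one randomised physician.
- **Volume.** Data sources: "Estimate 6 UTI treated visits per physician", giving the total of 30,438 records "to be included in the analysis". No time window is attached to the 6.
- **Analysis.** Section 5, item 3, places "Acute cystitis episodes = n" above the results table. The Crude OR is (c × h)/(g × d), from post-period counts. The Adjusted OR divides this by the baseline odds ratio (a × f)/(e × b). The text adds "Evaluation is a 4-way comparison", with the pre-to-post change in one group set against that in the other, and, on scope, "Do this for each of the four study comparisons listed in Section 4".
- **Interval.** A 95% CL column heading is all that is given. The text supplied contains no variance formula, regression model, robust standard error, bootstrap, ICC or paired method.

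**The concern.** Episodes treated by the same physician tend to resemble each other, and the same physician can supply episodes to both the pre and the post cells. Once counts are summed over an arm, both features are lost. An analyst who has only the eight totals can compute no limits other than those that treat every episode as independent.

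The 95% CL is the only measure of uncertainty shown for the four comparisons. If it is computed from the tabled counts, its width will generally be wrong, and a reader cannot tell from the plan in which direction. Leaving the method open also allows it to be chosen after the results are seen.

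**Working it through.** **The plan's own figures.** 1,691 × 3 = 5,073 physicians and 5,073 × 6 = 30,438 records. Both reproduce exactly.

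**What the estimator is.** The Adjusted OR equals [(c/d)/(a/b)] / [(g/h)/(e/f)], a ratio of two pre-to-post odds ratios. This is the arm-by-period term of a saturated logistic model.

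**Inputs that must be assumed.** The documents give no ICC, no coefficient of variation (CV) of physician volume and no correlation r between a physician's pre and post prescribing tendency. I take ICC 0.05 to 0.20, CV 0 to 1 and r 0.8 to 1.0. Mean episodes per physician per period, m, is taken as 2 to 3 (6 visits over three or two half-year windows). I also show m = 6, in case the 6 refers to a single period.

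**Formulas.** The variance ratio (VR) is true variance over count-based variance. The true type I error of a nominal 5% test is 2 × [1 − Φ(1.96/√VR)].

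- Crude OR, fixed sizes: VR = 1 + [m(1 + CV²) − 1] × ICC.
- Adjusted OR, Poisson-type volumes independent between periods given the physician: VR = 1 + m(1 + CV²)(1 − r) × ICC. Limits are too narrow whenever r < 1.
- Adjusted OR, each physician's volume the same pre and post: VR = 1 − ICC + m(1 + CV²)(1 − r) × ICC. Limits are too narrow only if m(1 + CV²)(1 − r) > 1.

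**Results.**

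| Estimate | Volumes | m | ICC | CV | r | VR | Type I error |
|---|---|---|---|---|---|---|---|
| Adjusted | matched | 2 or 3 | 0.20 | any | 1 | 1 − 0.20 = 0.80 | 2.8% |
| Adjusted | matched | 2 or 3 | 0.05 | any | 1 | 1 − 0.05 = 0.95 | 4.4% |
| Adjusted | matched | 3 | 0.20 | 0 | 0.8 | 0.80 + 3 × 0.2 × 0.20 = 0.92 | 4.1% |
| Adjusted | independent given physician | 2 or 3 | any | any | 1 | 1.00 | 5.0% |
| Adjusted | independent given physician | 2 | 0.20 | 1 | 0.8 | 1 + 2 × 2 × 0.2 × 0.20 = 1.16 | 6.9% |
| Adjusted | independent given physician | 3 | 0.20 | 1 | 0.8 | 1 + 3 × 2 × 0.2 × 0.20 = 1.24 | 7.8% |
| Adjusted | independent given physician | 6 | 0.20 | 1 | 0.8 | 1 + 6 × 2 × 0.2 × 0.20 = 1.48 | 10.7% |
| Crude | fixed | 3 | 0.05 | 0 to 1 | – | 1.10 to 1.25 | 6.2 to 8.0% |
| Crude | fixed | 3 | 0.20 | 0 to 1 | – | 1.40 to 2.00 | 9.8 to 16.6% |

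**Size on the standard-error scale.** At m = 3 the count-based SE of the log Adjusted OR is √[4/(1,691 × 3 × p(1 − p))]. This is 0.056 at an assumed event rate p of 0.5 and 0.061 at 0.3. Multiplying by √1.24 = 1.114 gives 0.063 and 0.068.

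**Simulation check.** Null data were simulated with 1,691 physicians in each of two arms, CV 1 and 6,000 replicates per setting (Monte Carlo error about 0.3 points). At m = 3, ICC 0.20 and r 0.8, count-based limits gave 7.6% (p 0.5) and 7.5% (p 0.3). With matched volumes and r 1, they gave 3.0% at ICC 0.20 and 4.4% at ICC 0.05. Physician-clustered robust limits gave 4.9 to 5.5% in all eight settings tried. On one simulated data set the eight-count formula and the model's arm-by-period OR agreed at 0.97569, with a count-based SE of 0.0559 and a robust SE of 0.0610.

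**The case against.** **The plan never says it will use independence limits.** This stands. The table is an empty shell, and the line above it may be only a slot for the episode count, not a declaration of the inferential unit. A reader might infer that the plan commits to a naive interval; the documents do not support that. The point is that the method is missing and that the only inputs on display lead to the wrong one.

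**The two cited papers may supply the method.** They are attached to the sentence saying that the odds ratio approximates the relative risk, and are listed again in a short reference list straight after the formulas. One is, by its title, a methods paper on measuring prescribing improvement in pragmatic trials. They may describe an interval, but the plan does not say that it takes one from them.

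**Dividing by the baseline odds ratio already removes the clustering.** This is partly right. It adjusts the point estimate and, where physician tendencies are stable, removes much of the extra variance. It does not supply a variance. A reader might also infer that count-based limits are always too narrow, or too narrow whenever tendencies shift. Neither holds for the Adjusted OR: with matched volumes at m = 3, ICC 0.20, CV 0 and r 0.8, tendencies shift and the limits are still too wide (VR 0.92).

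**The effect is small and rests on assumptions.** For the Adjusted OR at 2 to 3 episodes per period it is modest, and every driver is assumed. Even the volume is uncertain: the 6 counts treated visits, whereas the results table has a row for no treatment, so episodes per physician may exceed 6. This limits any claim about size. It does not make the limits correct.

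**Conclusion.** The point holds as an unspecified interval method in a trial randomised by physician, and it should be fixed. Confidence is high that the method is not stated and that limits built from the pooled counts would in general have the wrong width. Confidence in the size of the error is low.

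- **Crude OR:** count-based limits are too narrow at any positive ICC when physicians contribute more than one episode.
- **Adjusted OR:** the direction depends on ICC, r and how volumes vary between physicians and periods. Over the 2-to-3-episode range, the two extremes are matched volumes with fully stable tendencies, and variable volumes with r = 0.8.

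The documents do not support a claim that the planned analysis is badly anti-conservative, nor that the Adjusted OR is safe as it stands.

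**What to change.** Add to item 3, for each of the four comparisons:

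> The 95% CL for the Adjusted OR (and for the Crude OR if reported) is obtained with the physician as the cluster across both periods, from a logistic GEE on episodes with arm, period and arm-by-period terms, independence working correlation and physician-clustered robust standard errors.

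A bootstrap that resamples whole physicians, keeping both periods together, is an acceptable equivalent.

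The cost is one sentence and a few lines of code. The physician link is already needed to match diagnosing and prescribing physician. Because the model is saturated, the Crude and Adjusted OR point estimates do not change. The downside is that some intervals become wider, by about 11% in the least favourable Adjusted OR case at 3 episodes per period. Others may become narrower.
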